Study Design	
Study design: Pilot randomized, single site clinical trial with blinded analysis
 
Participant recruitment and study site: We will recruit participants interested in using the ENG contraceptive implant but not currently at risk for pregnancy from University of Utah Hospital and Community clinics, and through targeted social media ads. All study procedures will occur at the University of Utah Hospital Outpatient OBGYN Clinic
 
Sample size: This is a pilot proposal to recruit a total of 40 participants across 2 study arms: (1) ENG implant only (n=20) and (2) UPA + same day ENG implant insertion (n=20). Our null hypotheses are:
 
 
1) ENG implant along with UPA administration in the presence of a dominant ovarian follicle will not change the expected 97% ovulation suppression within 5 days of UPA use.
 
2) ENG implant insertion alone in the presence of a dominant ovarian follicle will not sufficiently interrupt ovulation.
 
 
Inclusion criteria: Healthy people, age 18-35 years, fluent in English and/or Spanish, BMI < 30 kg/m^2, no known contraindication to either the ENG contraceptive implant or UPA using the CDC Medical Eligibility Criteria for Contraceptive Use 2016, not currently pregnant and not at risk of pregnancy (defined as not having penile-vaginal intercourse or using a non-hormonal method of contraception such as a barrier method, condoms, diaphragm, or cervical cap, a copper IUD, or permanent contraception), know the date of their last menstrual period, have a regular menstrual cycle (24-35 days), be willing to comply with the study requirements, and be willing to avoid pregnancy for study duration.
 
Exclusion criteria: Current pregnancy or breastfeeding, use of hormonal contraception or exogenous hormones (estrogen, progestogen, or HCG) in the last month (or past 6 months for depo medroxyprogesterone acetate) planned use during the study, vaginal bleeding of unknown etiology, allergy to UPA or ENG, regular or planned use of glucocorticoids during the study, or current or planned use of any medication that potentially interacts with UPA or ENG.
 
Participant adherence: Screening protocol will ensure willingness to comply with all study procedures. Participants will receive compensation for each component of the protocol.

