Study Flowchart	<pre> graph TD     A[Phone Screening for Eligibility] --> B[Screening Visit 1- history, exam, TVUS]     B --> C[Screening Visit 2- Day 20-24 progesterone]     C --> D[Screening Visit 3-7 (+/-2)- Start TVUS 3X/week on day 7, then daily when follicle ≥ 13mm]     D --> E[Treatment Visit 1 (Follicle ≥ 14mm) – Randomization TVUS, serum LH, P4 and E2]     E --> F[Group 1- ENG Implant]     E --> G[Group 2- oral UPA + ENG Implant]     F --> H[Treatment Visit 2-8 (days 2,3,4,5,6,7,8)- TVUS, serum LH, P4 and E2]     G --> H     H --> I[Exit Visit (Treatment Day 14)- TVUS, serum LH, P4 and E2]   </pre>

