
Statistical Analysis Plan
	
The investigator and study team will be responsible for analyzing the study data. The official clinical database in RedCAP will not be analyzed until medical/scientific review has been completed, protocol violators have been identified (if appropriate), and data has been declared complete.
 
Variables/Time Points of Interest
 
The primary outcome is delay in rupture of the dominant follicle by 5 days (yes/no) between group 1 (ENG implant alone) and group 2 (UPA with same day ENG implant). If the date of follicle rupture was unclear by ultrasound alone, we will utilize serum hormone levels to adjudicate day of rupture. These measures include day of follicle collapse, day and value of highest LH, day and value of highest progesterone level. We will use an estradiol level of >100pg/ml to confirm the enlarged follicle is the dominant follicle on the treatment day.
 
Statistical Methods
 
The primary and secondary dichotomous outcome measures of ovulation by 5 days will be assessed by Wilcoxon sign rank test and demographic will be analyzed using descriptive statistics.
 
Power/Sample Size:
 
This is a pilot study to obtain point estimates for future study proposals. Current data on ovulatory function with mid-cycle implant insertion or the pharmacodynamics interactions between same day UPA and ENG are lacking.

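### Should the pilot stratify by, adjust for, or commit to describing follicle diameter and LH at randomisation?

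*Combined protocol and SAP*

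**What the plan says.** The Study Design section plans 20 participants on the etonogestrel (ENG) implant alone and 20 on ulipristal (UPA) plus same-day implant. Study Procedures randomises in blocks of four and names no stratification factor. Entry requires a lead follicle of at least 14 mm. Scans are three times a week at first and become daily once the follicle passes 13 mm.

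The Study Flowchart lists for Treatment Visit 1: "Randomization TVUS, serum LH, P4 and E2". Diameter and LH are therefore scheduled for every participant at randomisation.

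The SAP gives the primary outcome as "delay in rupture of the dominant follicle by 5 days (yes/no) between group 1 (ENG implant alone) and group 2". Among the hormone measures, "day and value of highest LH" helps to date a rupture that ultrasound leaves unclear, and estradiol serves to "confirm the enlarged follicle is the dominant follicle on the treatment day". On analysis, the SAP says that "outcome measures of ovulation by 5 days will be assessed by Wilcoxon sign rank test and demographic will be analyzed using descriptive statistics". On purpose: "This is a pilot study to obtain point estimates for future study proposals".

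The two null hypotheses in Study Design each concern one regimen. The combination "will not change the expected 97% ovulation suppression within 5 days of UPA use", and the implant alone "in the presence of a dominant ovarian follicle will not sufficiently interrupt ovulation".

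**The concern.** How close a follicle is to rupture at randomisation could plausibly affect whether it ruptures within five days. The 14 mm gate has no upper limit and no LH condition, so participants may enter at different stages. Nothing in the randomisation or the analysis balances stage or corrects for it, and no table is promised that would show an imbalance.

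The pilot exists to supply rates for later proposals, and the SAP itself says that data on mid-cycle insertion are lacking. An ENG-alone rate from an unusually early or late set of follicles could mislead the next design. A reader would also not know which follicle sizes the rate applies to.

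**Working it through.** **Inputs from the documents.** 20 per arm; 97% expected suppression with UPA (Study Design); blocks of four, unstratified (Study Procedures). The SAP gives no power calculation, so there is no planned figure to reproduce beyond 20 + 20 = 40.

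**Assumed inputs.** The documents give neither the share of advanced follicles nor their prognostic strength. I take 20-50% advanced. For ENG alone, the five-day no-rupture rate is 0.5-0.6 (early) v 0.1 (advanced) as strong prognosis, and 0.5 v 0.3 as weaker. UPA plus ENG is 0.97 at either stage.

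**1. How often are the arms imbalanced?** Let X1 and X2 be independent Binomial(20, q) counts of advanced follicles in the two arms. Blocks of four do not balance an unstratified factor.

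| q | P(abs(X1 - X2) ≥ 4) |
|---|---|
| 0.20 | 0.164 |
| 0.30 | 0.226 |
| 0.40 | 0.258 |
| 0.50 | 0.268 |

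**2. How far does that move the estimate?** By symmetry, half of an imbalance D falls in the ENG arm on average, so its rate moves by (D/2)/20 × gap = D × gap/40. Given D ≥ 4, the mean of D under the same binomials is 4.71 at q = 0.2 and 5.12 at q = 0.5.
- Strong prognosis: from 4.71 × 0.4/40 = 0.047 to 5.12 × 0.5/40 = 0.064.
- Weaker prognosis: 4.71 × 0.2/40 = 0.024 to 5.12 × 0.2/40 = 0.026.

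**3. Against what uncertainty?** Half-width = 1.96 × sqrt[p(1 - p)/20 + 0.97 × 0.03/20], where p is the overall ENG rate.
- q = 0.2, 0.5 v 0.1: p = 0.8 × 0.5 + 0.2 × 0.1 = 0.42, half-width 0.229; 0.047/0.229 = 0.21.
- q = 0.5, 0.6 v 0.1: p = 0.35, half-width 0.222; 0.064/0.222 = 0.29.

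The average shift in an imbalanced trial is thus a fifth to under a third of the half-width. That interval already includes the variation from chance imbalance. In a simulation with a continuous diameter (20,000 trials), the unadjusted interval covered the truth in 93.6-95.5% of trials.

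**4. What would adjustment gain?** Simulation of 100,000 trials per setting, one binary stage term. The first two columns of results concern trials with an imbalance of four or more.

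| ENG early v advanced | Mean absolute error, unadjusted v adjusted | Adjusted estimate farther from truth | Variance change, all trials |
|---|---|---|---|
| 0.5-0.6 v 0.1 | 0.095-0.104 v 0.088-0.099 | 40-45% | none to 8.8% lower |
| 0.5 v 0.3 | 0.093-0.096 v 0.096-0.100 | 48-53% | 1.1-2.2% higher |
| not prognostic (0.4) | not tabulated | not tabulated | 2.8-2.9% higher |

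Even in the strong range there is no gain at 20% advanced with 0.5 v 0.1 (0.097 v 0.098). With an overall ENG rate of 0.4, adjustment breaks even only when the stage-specific ENG rates differ by about 25-41 points.

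**5. Would adjustment reach the estimate at risk?** In this model the whole shift comes through the ENG-alone rate. A covariate-adjusted risk difference leaves that rate as observed, although the second null hypothesis is about that rate.

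**The case for a change.** The best case for a change rests on the table. Both hypotheses are conditional on a dominant follicle, and a rate carried into a future proposal should say what follicles it came from. That holds even if the arms are balanced and whether or not stage is prognostic. Two baseline rows cost nothing to collect. Fixing them in advance also limits later choice of a covariate or cut-point, since the study team analyses its own data.

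As reporting practice this stands. It does not show a fault in the plan. Diameter and LH are collected at the randomisation visit and recorded for each visit, and nothing bars tabulating them. The SAP says that demographics will be described; it does not say that nothing else will be. An analyst reporting a follicle study would ordinarily show follicle size at entry. An analyst who tabulates LH should check whether the Day 1 sample preceded treatment, which Study Procedures leaves open.

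The point about later choice of a covariate would matter if an adjusted figure were to carry weight. Here the planned comparison is unadjusted. At 97% suppression only 20 × 0.03 = 0.6 ruptures are expected in the combination arm, with probability 0.97^20 = 0.54 of none, so an adjusted figure could not replace it.

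Leaving 40 participants unstratified is a normal choice, and daily scanning past 13 mm narrows the spread of diameter at entry, though it does not constrain LH. The sentence quoted from Statistical Methods also names a signed-rank test, a paired procedure, for two independent groups. That is a separate matter, and the point about baseline variables neither depends on it nor resolves it.

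**Conclusion.** No change to the plan follows. The description of the text is accurate: Day 1 diameter and LH have no stated role as baseline variables. The consequence is random error, neither bias nor inflated type I error. Under assumed strong prognosis it is a 5-6 point average shift in the 16-27% of trials with a marked imbalance, inside a 21-23 point half-width; under weaker prognosis the shift is about 2-3 points.

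The missing baseline rows are a gap that analysts can fill sensibly from data already collected. Adjustment is a trade-off without assured gain: variance between about 9% lower and 3% higher, with the ENG-alone rate untouched.

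These sizes rest on the assumed share of advanced follicles, their prognostic strength, and UPA plus ENG at 97% whatever the stage. The statement that no other role is given covers only the supplied text. If follicle stage were far more prognostic than assumed here, adjustment would gain more, but the planned estimate would still be unbiased.
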